2.1 Description of Device

SuperSaturated Oxygen Therapy (“SSO₂ Therapy”) is an adjunctive cardiac catheterization laboratory initiated procedure with superoxygenated blood delivered via a qualified delivery catheter to the left main coronary artery (LMCA) in a patient with acute myocardial infarction (AMI) after successful percutaneous intervention (PCI) with stenting has been performed. The equipment necessary for SSO₂ Therapy is comprised of three components: the DownStream® System (“system”), the DownStream® Cartridge (“cartridge”), and the SSO₂ delivery catheter (“delivery catheter”). The system and cartridge function together to create a highly oxygen-enriched saline solution called SuperSaturated Oxygen solution (“SSO₂ solution”). A small amount of autologous blood is mixed with the SSO₂ solution producing oxygen-enriched hyperoxic blood which is then delivered to the LMCA via the SSO₂ delivery catheter at a flow rate of 100 ml/min. The duration of SSO₂ Therapy is 60 minutes as detailed in this protocol.

2.1.1 DownStream System

The system is the electromechanical device (console) that controls the cartridge and monitors performance and safety during administration of SSO₂ Therapy. The system has safety features that continuously monitor system parameters such as the blood flow rate and pressure, and detect potentially unsafe conditions such as the presence of air-in-line. A display screen guides the health care professional through setup and clinical operation. The system is non-sterile and has no direct contact with the patient or the blood flow path. The system is intended to be mains-operated (AC-powered) and stationary during use but is equipped with battery backup power. The system is designed for operation in a cardiac

catheterization laboratory and must be operated and monitored by trained personnel when providing SSO₂ Therapy. The DownStream System is shown in **Figure 1a** and **Figure 1b** (closeup).

Figure 1a. TherOx® DownStream® System

[figure not shown]

Figure 1b. Close-up of DownStream® System Components

The major subsystems of the DownStream System are the Cartridge Control Subsystem (“CCS”), Display Subsystem (“Display”), Power Supply Subsystem (“Power Supply”), and Oxygen Supply Subsystem (“Oxygen Supply”).

The CCS monitors and controls the operation of the cartridge during operation. The CCS has a cartridge housing that contains the cartridge. An oxygen valve controls the flow of oxygen to the cartridge from the E-bottle source that is securely mounted onto the system. A piston actuator operates the piston (syringe) inside the cartridge to withdraw saline from the IV bag and pump it into the cartridge to make superoxygenated saline. A peristaltic blood pump operates on the cartridge draw tubing to withdraw arterial blood from the patient and pump it through the cartridge, returning hyperoxic blood back to the patient. A modular jack on the front panel of the CCS connects to the cartridge transducer assembly. The transducer communicates with the system and is written to after use to prevent re-use. An ultrasonic probe (for bubble/air in line detection and flow monitoring) and return clamp on the front panel of the CCS operate on the Cartridge Return tubing. A Prime switch and Emergency Stop switch located on the Display are also part of the CCS.

The Display Subsystem located at the top of the system is the user interface. A keypad provides user control of system operation. An LCD display provides visual feedback, and a speaker provides audible feedback for the user. Users are cardiologists and nurses administering the treatment in the cardiac catheterization laboratory (CCL). The user has seven keys (buttons) on the Display Subsystem that control system operation. An LCD display provides visual feedback, and a speaker provides audible feedback for the user.

The Power Supply Subsystem is an electronic assembly that provides DC power to the CCS and Display Subsystems. The Power Supply receives power from the AC Mains or an internal battery. Component features of the Power Supply include: appliance inlet receptacle with fuses, medical grade 15 VDC power supply, battery charger, DC-to-DC power supplies, and a battery. The battery provides at least one half hour of system operation when fully charged. When connected to AC Mains, the system automatically charges the battery.

The Oxygen Supply Subsystem is a mechanical assembly that provides regulated oxygen to the CCS. The Oxygen Supply uses pressurized oxygen from a medical grade E-bottle, which it regulates to 750 ± 50 psig. Component features of the Oxygen Supply include: E-bottle (yoke-type) connection, oxygen regulator with 900 psi relief valve, bottle pressure

gauge, and oxygen filter. The Oxygen Supply can support over 50 treatments on one E-bottle.

2.1.2 DownStream Cartridge

The cartridge is a single-use disposable device that is loaded into the system by a trained healthcare professional. The cartridge has a three-chambered body that creates SSO₂ solution from inputs of hospital-supplied oxygen and physiologic saline and mixes the SSO₂ solution with arterial blood within the cartridge blood path. The cartridge has a tube set that draws the patient's arterial blood through the draw line, and returns oxygen-enriched hyperoxicemic blood through the return line to the SSO₂ delivery catheter. The cartridge draw line connects to the sidearm of an arterial sheath. Sheath placement may be coaxial (single arterial access site) or contralateral (two arterial access sites) at the physician's discretion. A physician makes two line connections during the initiation of SSO₂ Therapy: the cartridge draw line is attached to the arterial sheath before priming the blood flow path, and the return line is attached to the SSO₂ delivery catheter after the blood flow path is successfully primed. The priming volume of the cartridge is approximately 60 ml. The cartridge is shown in **Figure 2**.

[figure not shown]

Figure 2. TherOx® DownStream® Cartridge

A fluid manifold in the Oxygen Chamber provides the fluid path between the three chambers. The IV tubing set connects the Piston Chamber to a 1-liter bag of sterile saline provided by the hospital. The draw tubing set connects the blood mixing chamber to an arterial draw sheath (blood from the patient), and the return tubing set connects the blood mixing chamber to the delivery catheter (hyperoxic blood to the patient). **Figure 3** depicts the fluid flow paths through the cartridge and the fluid flow control features.

[figure not shown]

Figure 3. DownStream® Cartridge Fluid Flow Path

The DownStream Cartridge utilizes medical grade polyvinyl chloride ("PVC") tubing for blood withdrawal and return to the patient. The cartridge housing is constructed primarily of injection-molded medical grade polycarbonate, a common plastic material used in medical devices. The tubing and Blood Mixing Chamber ("BMC") comprise the blood-wetted fluid path of the cartridge.

The production and flow of SSO₂ solution are continuous within the DownStream Cartridge; control of these processes is maintained through the use of the Fluid Manifold shown in **Figure 3**. The Fluid Manifold connects and controls the flow of saline and SSO₂ solution between the three chambers of the cartridge with three needle valves and one check valve. The Piston Chamber delivers saline to the Fluid Manifold through a small tube. The

saline can be delivered to the Oxygen Chamber through the atomizer to create SSO₂ solution, through a dilution port to adjust concentration, or directly to the BMC to flush the capillary tube. The SSO₂ solution's dissolved oxygen concentration is controlled by the DownStream System.

The DownStream Cartridge is equipped with a pressure transducer that monitors the blood mixing chamber pressure in the device during operation; the transducer connects to the DownStream System. An IV spike and flexible tube are attached to the Piston Chamber, enabling easy connection to an IV bag during the procedure. The draw and return tubing are equipped with luer connections. The DownStream Cartridge is a single-use Ethylene Oxide (“EO”)-sterilized device.

The draw tubing is connected to the patient with a luer fitting that is attached to the femoral access sheath. The return tube is attached to the SSO₂ delivery catheter that has been placed in the ostium of the left main coronary artery.

2.1.3 SSO₂ Delivery Catheter

The SSO₂ delivery catheter is a 5F (O.D.) over-the-wire catheter that is equipped with a standard luer fitting at the proximal end for attachment to the return line of the cartridge. The SSO₂ delivery catheter has a total length of 100 cm and is placed over a guidewire to reach the coronary vasculature. During administration of SSO₂ Therapy, the SSO₂ delivery catheter is placed in the ostium of the LMCA and connected to the cartridge by the trained physician.

Only a catheter that is qualified by TherOx may be used as the SSO₂ delivery catheter. The qualified SSO₂ delivery catheter is the 5F Boston Scientific Impulse[®] angiographic catheter. Superoxygenated blood may not be infused with a non-qualified catheter because of the risk of bubble nucleation and the introduction of air emboli to the patient, therefore the use of a non-qualified delivery catheter is contraindicated. TherOx has qualified the 5F Boston Scientific Impulse[®] for compatibility with superoxygenated blood and this catheter must be used in this study.

2.1.4 Patient Connections

The DownStream Cartridge draw tubing connects to a femoral arterial sheath that may be used for angioplasty and stenting procedures. Sheath placement may be coaxial (using one femoral arterial access site) or contralateral (using both the right and left femoral arteries for

access sites), at the physician's discretion. A single sheath is recommended as prior studies have shown that single femoral artery access, even with a larger sheath, results in less bleeding and fewer vascular complications than bilateral femoral access. In the preferred coaxial configuration, a single introducer sheath can be used. The DownStream Cartridge draw tubing luer fitting connects to the sheath sidearm. The SSO₂ delivery catheter (the 5F Boston Scientific Impulse[®] angiographic catheter) is placed to the ostium of the left main coronary artery using standard cath lab techniques. When extracorporeal blood flow is initiated, the delivery catheter and DownStream Cartridge return tubing are wet-connected to ensure that no gaseous emboli are introduced to the patient during priming. The cartridge return tubing luer fitting connects to the luer hub of the delivery catheter. For the contralateral approach, a 5F introducer sheath is used in a second femoral access site for blood withdrawal. This alternative approach may be used by physicians who prefer to use two smaller sheaths for arterial access instead of a single sheath.

Figure 4 provides a schematic of the patient connections during SSO₂ Therapy administration.

[figure not shown]

Figure 4. Patient Connections

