7.4 SSO₂ Therapy

7.4.1 Arterial Sheath Selection

The coaxial (single arterial stick) approach is strongly recommended for SSO₂ Therapy as prior studies have shown that single femoral artery access, even with a larger sheath, results in less bleeding and fewer vascular complications than bilateral femoral access. When only one arterial site (coaxial access) is used with the DownStream System, an 8F sheath may be used, or a qualified 7F sheath⁶. Contralateral access with a second sheath may be used as an alternative if desired, in which case a smaller 5F introducer sheath in the contralateral femoral artery may be used. Ipsilateral insertion of a second sheath into the same femoral artery is strictly prohibited.

The TherOx SSO₂ delivery catheter requires a qualified 7F or 8F arterial sheath for coaxial setup because of the need for an adequate blood flow path for blood withdrawal between the catheter and sheath. If contralateral access is preferred, a minimum 5F sheath is required to withdraw blood from the second arterial access site.

If a 5-6F radial sheath was used for PCI, a second 5F sheath should be placed in a femoral artery for blood withdrawal.

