- Vascular damage from the placement of an infusion catheter
- Bleeding requiring treatment, particularly at the catheterization site

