8.6 Clinical Events Committee (CEC)

During the course of the study, an independent Clinical Events Committee (CEC) will be responsible for the adjudication of clinical events.

The CEC shall consist of three members with the appropriate medical background in cardiology, including at least one interventional cardiologist, and will be appointed by the Sponsor. The CEC must consist of individuals who are impartial, independent of the investigator(s) and who have no financial, scientific, or other conflict of interest with the study. Written documentation attesting to absence of conflict of interest will be required.

Should a CEC member not be able to fulfill their commitment to the committee and the study for any reason, another member will be appointed to replace them according to the qualifications noted above.

The CEC is responsible for adjudicating protocol-defined adverse events. The committee determines whether the reported events meet the established definitions for the adverse events that will be tracked in this study. This process includes a thorough review of the source documents for the event and an independent adjudication of the event according to protocol definitions.

The CEC may or may not agree with conclusions drawn by the investigator from a specific investigational site; in this case, the CEC's conclusion will serve as the final decision for submission to regulatory authorities and for reporting and publication. Furthermore, should the committee members become aware of an event through the review of source documents from the research subjects, they will be able to adjudicate those events even if the site investigator has not reported them.

In the course of reviewing an event, the CEC will determine the following:

- Agreement or disagreement with event as reported by the study investigator
- Adverse event classification
- Relation of adverse event to investigational device
- Need for additional data

Events to be adjudicated for this study include:

- **Disease specific:**
 - Death (cardiac death, vascular death, non-cardiac death; if the cause of death is unknown it will be adjudicated as cardiac death)
 - Revascularization (PCI or CABG): clinically driven, non-clinically driven
 - Recurrent angina or reinfarction (Q-wave MI, Non-Q-wave MI, target vessel related, non-target vessel related)

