 - Arrhythmias (2nd and third degree heart block, atrial fibrillation, flutter or supraventricular tachyarrhythmias, non-sustained or sustained ventricular tachycardia or fibrillation)
 - Cerebrovascular accident (including stroke and TIA)
 - Stent thrombosis (ARC definite or probable)
 - New onset heart failure
 - Hospital readmissions (cardiac heart failure related, cardiac non-heart failure related, non-cardiac)
 - Embolism (including air emboli and thromboemboli)
 - All bleeding (TIMI scale and BARC scale) and blood product transfusions
- **Procedure related:**
 - Vascular complications: access site hematoma, pseudoaneurysm, arteriovenous fistula peripheral ischemia or nerve injury
 - Bleeding complications, including Intracerebral Hemorrhage (ICH), and Hemolysis
 - Need for surgical intervention at the access site
 - Transfusion
 - Infection
- **Device specific:**
 - Dislodgement of the device requiring repositioning
 - Dissection of the LMCA or its branches
 - Thrombosis (including catheter thrombus)
 - Intra-procedural ischemia related to catheter position in LMCA
 - Any clinically-driven discontinuation of SSO₂ Therapy before 60 minutes

The CEC charter is included in **Appendix F** of the Investigational Plan.

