#### **6.5.6. Safety Assessment**

All adverse events will be recorded and tabulated and grouped by event type overall, and by visit; occurring in-hospital, at the 30-day visit, and post-30 days through 1 year.

An independent Clinical Events Committee will adjudicate any suspected NACE events, cardiac adverse events, vascular events, bleeding, and other events that may have a device relationship. Adverse events will further be categorized as serious or not serious and as primary events or associative symptoms/events.

An adverse event is defined as serious whenever the adverse event is fatal, life-threatening, disabling, results in patient hospitalization or prolongation of hospitalization, or requires medical intervention to prevent permanent impairment of a body structure or function.

Events will be further grouped according to diagnosis when the diagnosis is identified by the reporter. The diagnosis will be categorized as the Primary Event. Associative events are defined as reported/coded events (*e.g.*, signs/symptoms) associated with a precipitating primary event/diagnosis (*e.g.*, a primary event/diagnosis of GI bleed with associative events of nausea, hematemesis, and anemia).

Incidence of adverse events for each reporting period will be tabulated (number and percentage) overall and by categorization up to the 1 month (30 day) follow up visit. Further, adverse events will be summarized by relationship to the investigational device, interventional procedure, and disease.

The in-hospital and 30-day clinical outcomes, including the composite Net Adverse Cardiac Events (NACE) rate, the composite Target Vessel Failure (TVF) rate, the individual NACE and TVF component event rates, as well as the rate of other protocol-specified events requiring adjudication will be similarly tabulated for all CEC adjudicated events as well as all site-reported events.

The critical safety data to be evaluated in this trial, including death, myocardial rupture, stent occlusion and SAE bleeding through 30 day follow-up, will be tabulated overall and by onset period (intraprocedure, prior to discharge, discharge to 30 days). The observed event rates for each component event type will be assessed in comparison to the FDA guideline for acceptable critical safety event rates, and with respect to individual patient circumstances for each event. Relative frequency and 95% confidence interval will be computed for each event type.

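### The relationship tables cannot isolate, and may understate, access-site harm added by SSO₂, because *interventional procedure* is undefined and the draw sheath is not part of the device

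*Protocol*

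**What the plan says.** **Device.** Protocol 2.1: "The equipment necessary for SSO₂ Therapy is comprised of three components". These are the system, the cartridge and the delivery catheter. The risk analysis in Protocol 8.1 covers the same three. The arterial sheath is not among them.

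**Access.** Protocol 2.1.4 allows a two-site set-up: "For the contralateral approach, a 5F introducer sheath is used in a second femoral access site for blood withdrawal". Protocol 7.4.1 adds: "If a 5-6F radial sheath was used for PCI, a second 5F sheath should be placed in a femoral artery for blood withdrawal". The single-site (coaxial) set-up is strongly recommended and uses an 8F or a qualified 7F sheath.

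**Expected harm.** Among the risks that SSO₂ may increase, Protocol 8.1 lists: "Bleeding requiring treatment, particularly at the catheterization site". The reasons given are longer cath-lab time, the anticoagulation that goes with it, and the extracorporeal circuit.

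**Attribution.** Among the things the Clinical Events Committee (CEC) must determine, Protocol 8.6 and SAP 4.1 list: "Relation of adverse event to investigational device". No corresponding item is given for a procedure. SAP 6.5.6 then says that "adverse events will be summarized by relationship to the investigational device, interventional procedure, and disease".

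**The concern.** The trial has one arm. With no concurrent PCI-only group, judging what caused each event is the main means within the trial of separating harm added by SSO₂ from harm that PCI would have caused anyway. Protocol 9.2 and SAP 2.1 say that FDA's review of death, stent thrombosis, myocardial rupture and bleeding will take into account how each event relates to the study device.

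A bleed or pseudoaneurysm at a femoral site opened only to draw blood for SSO₂ is a harm of the therapy, but it has no clear place in the planned table. The sheath is not a device component, and the procedure row may or may not mean PCI. If such events go to a row that is read as PCI, the device-related row omits a harm that the protocol itself anticipates, and the published table does not let a reader recover it.

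**Working it through.** The documents state no figure for this point, so the check is a comparison of sections.

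1. **Can access exist only because of SSO₂?** Yes. After radial PCI, 7.4.1 says that "a second 5F sheath should be placed in a femoral artery for blood withdrawal"; PCI itself did not use that puncture. The contralateral sheath in 2.1.4 is a second case, at the physician's discretion. The coaxial case is different: 2.1.4 lets the draw sheath be the one used for PCI, so a complication there is shared.

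2. **Is that access part of the device?** Not by the component list in 2.1 or the scope of the risk analysis in 8.1. The cartridge draw line connects to the sheath, but the sheath is not listed.

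3. **Does the relationship table have a row for it?** SAP 6.5.6 has three rows: device, interventional procedure and disease. The protocol and SAP text do not define the second. Elsewhere the two procedures are kept apart: SAP 6.5.3 tabulates the index PCI separately from SSO₂ procedure data and puts arterial access variables with the latter. That distinction is missing from the relationship table.

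4. **What follows for one event at SSO₂-only access?** Under the present wording it can be coded to the device, or to a row that mixes PCI and SSO₂. In the first case it is counted as SSO₂ harm. In the second it drops out of the device row and cannot be told apart from a PCI event. For these events, then, the ambiguity can lower the device-related rate but cannot raise it.

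5. **What does not change?** NACE (Protocol 9.2, SAP 2.1) includes TIMI major or minor bleeding with no relationship condition, and so does the 3.0% bleeding guideline. Both rates are the same under either coding.

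6. **Scale, for illustration only.** Suppose *k* of the 100 patients have a complication at SSO₂-only access. Coded to the procedure row, these add 0 to the device row; attributed to SSO₂, they add *k*/100. SAP 6.1 uses Jeffreys 95% intervals, that is, the 2.5th and 97.5th percentiles of Beta(*k* + 0.5, 100 − *k* + 0.5):

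| *k* (assumed) | Rate | Jeffreys 95% interval |
|---|---|---|
| 1 | 1.0% | 0.1% to 4.6% |
| 2 | 2.0% | 0.4% to 6.3% |
| 4 | 4.0% | 1.4% to 9.2% |

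No value of *k* can be taken from the documents.

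7. **A related timing gap.** Protocol 8.3 starts adverse event collection, and the SSO₂ procedure itself, at insertion of the delivery catheter. Section 7.4.2 lists the draw sheath (step 2) before the catheter (step 3). A complication that arises as an SSO₂-only sheath is inserted could fall before collection starts.

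**The case against.** The other side has a good case against any stronger claim.

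- A reader might infer that the CEC lists assign access-site harm to the background procedure, because "Vascular complications: access site hematoma, pseudoaneurysm, arteriovenous fistula peripheral ischemia or nerve injury" stands under the procedure-related heading and the device-specific list has no access-site item. The lists do not do that. They name events to be adjudicated, and all bleeding also stands under the disease-specific heading, so the headings cannot be exclusive causes.
- A reader might infer that the tables do understate SSO₂ harm. That is not shown. The protocol itself calls SSO₂ delivery a procedure, so the undefined term may include it. Protocol 4.5 gives the CEC the coding of relationships in general, and SAP 6.5.6 has it adjudicate vascular events, bleeding and anything else that might be linked to the device. Nothing stops it from attributing a draw-sheath bleed to the device.
- The CEC charter (Appendix F) and the case report forms (Appendix A) are not in the text reviewed. Either could hold a relationship definition or an access-site field.
- Coaxial access is preferred, so SSO₂-only access may be uncommon. FDA also reviews individual patient circumstances, and by-subject listings are planned.

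All of this stands. It reduces the claim from *understates* to *may understate*. It does not supply the missing category: even with careful adjudication, the three rows as specified cannot show SSO₂-procedure harm separately from PCI harm.

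**Conclusion.** The point holds in limited form. As written, the relationship tables cannot isolate access-site bleeding and vascular harm added by SSO₂, and they may understate it. The effect is confined to those tables and to reviews that rely on them; the success criterion and the 3.0% bleeding guideline are untouched. It is worth correcting but does not threaten the primary result.

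The size cannot be estimated. It might be tempting to apply an assumed share to the AMIHOT II bleeding rate (8/222 = 3.6%) and set the result against the bleeding guideline. The documents do not support that: no share is given, the 3.6% is not broken down by site, the earlier trials infused for 90 minutes through a catheter in the infarct artery, SAP 2.1 expects lower event rates now, and recoding would not move the guideline rate.

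The conclusion assumes that neither the CEC charter nor the case report forms already define an SSO₂-procedure relationship. If they do, the remaining task is to carry that definition into the SAP table.

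**What to change.** In Protocol 8.6 and SAP 4.1 and 6.5.6:

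- Replace *interventional procedure* with two categories, *PCI procedure* and *SSO₂ Therapy procedure*. Define the second, for attribution, to cover any arterial sheath placed, enlarged or retained for SSO₂ and any anticoagulation extended for it. State that it includes sheath insertion before the delivery catheter, and align the start of event collection in Protocol 8.3 with that.
- Have the CEC determine the relation of each event to the device and to each procedure.
- Record the access site of every bleeding or vascular event, if the case report form does not already do so.
- Report events related to the device or the SSO₂ procedure alongside the device-only rate.
- Tabulate TIMI and BARC bleeding and vascular complications by access set-up (coaxial, bilateral femoral, radial PCI with femoral draw), using the arterial access variables in SAP 6.5.3. Confirm that those variables distinguish the three set-ups.

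The cost is SAP and CEC form wording and at most one field on the event form. Clinical management does not change. The downside for the sponsor is that the reported SSO₂-related rate may be slightly higher.
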